3.5.2 Prohibited Concomitant Medications

[REDACTED]

| Medications | Washout Period |
|-------------|----------------|
| [REDACTED] | [REDACTED] |
| [REDACTED] | [REDACTED] |
| [REDACTED] | [REDACTED] |
| [REDACTED] | [REDACTED] |

[REDACTED]

3.6 Procedures for Monitoring Subject Compliance

Subjects will be admitted to the clinical trial site when experiencing an acute flare of urticaria symptoms or chronic spontaneous urticaria and will remain in the clinic for at least 2 hours to complete efficacy assessments and safety assessments. Subjects may be discharged once the discharge criteria is met.

4.0 STUDY POPULATION

The study population will be male or female adult volunteers aged 18 to 65 years diagnosed with urticaria who experience an acute flare of symptoms or have chronic spontaneous urticaria at least two (2) times a week while on a chronic treatment regimen and who have consented to participate in this study.

4.1 Inclusion Criteria

For a subject to be eligible for this study, he or she must meet **all** of the following criteria:

1. Is a male or female subject between the ages of 18 and 65 years, inclusive.
2. Has been clinically diagnosed with acute flares or with chronic spontaneous urticaria with unknown etiology and have urticaria symptom (patient-rated pruritus and hive severity score ≥ 2) at least two (2) times a week while on a chronic treatment (e.g., antihistamine) at least 2 weeks before dosing and will remain the same throughout the study.
3. Has body weight more than 30 kg and body mass index between 18 and 34 kg/m², inclusive.
4. Has no medical history of hypertension and cardiovascular disease in the last 10 years. Controlled hypertension without beta blocker confirmed by the Investigator is acceptable.
5. At screening, has stable vital signs in the following ranges (after 5 minutes of rest):
 - SBP ≥ 90 and ≤ 140 mmHg
 - DBP ≥ 50 and ≤ 90 mmHg
 - HR ≥ 45 and ≤ 100 bpm

Note: Each BP should be taken after at least 5 minutes rest in a chair with back supported, legs uncrossed, and upper arm bared (slight recline for comfort is permitted). If vital signs are out of range, the Investigator may obtain two additional readings, so that up to 3 consecutive assessments are made within 1 hour.

6. If female, is not pregnant or breastfeeding based on the following:
 - a. agree to the use of highly effective contraceptive methods for at least 2 weeks before baseline until 7 days after the last day of study drug and a negative urine pregnancy test at screening; or
 - b. is of nonchildbearing potential defined as clinically infertile as the result of surgical sterilization (hysterectomy, bilateral tubal ligation, bilateral salpingectomy and/or bilateral oophorectomy); or

- c. is confirmed postmenopausal status (defined as either having amenorrhea for ≥ 12 consecutive months without another cause and documented serum follicle-stimulating hormone (FSH) level > 40 mIU/mL or another documented medical condition (e.g., was born without a uterus)).

NOTE: The following are considered highly effective contraceptive methods: abstinence, hormonal oral contraceptives, injectables, and patches; intrauterine devices; double-barrier methods (synthetic condom, diaphragm, or cervical cap used with spermicidal foam, cream, or gel); Nexplanon contraceptive implant (if implanted within 3 years); and male partner sterilization.

- 7. If male (with or without vasectomy), agree to the use of highly effective contraceptive methods (as listed in Criterion #6 above) at screening until 7 days after the last day of study drug.
- 8. Is able to communicate clearly with the Investigator and staff; able to read, complete questionnaires, and understand study procedures.
- 9. Is willing and able to provide written informed consent prior to participating in the study.

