3.3 Efficacy Assessments

The following efficacy assessments will be evaluated based on self-reported and clinical assessments of pruritus at pre-dose, and at 5 (± 2 min), 10 (± 2 min), 15 (± 3 min), 30 (± 5 min), 45 (± 5 min), 60 (± 10 min), 120 (± 10 min) minutes, and every 60 minutes (± 10 min) after dosing until the discharge criteria (the time when symptoms of acute urticaria have been effectively treated based on the investigator's or his/her designee's opinion will be recorded, not necessarily when subjects discharged) is met for acute flare and until urticaria symptoms returns to the baseline for chronic spontaneous urticaria. If the time to return to baseline for chronic spontaneous urticaria is beyond 4 hours, such time may be recorded by the patient and reported in the follow-up call. The actual time of the assessment and of when the symptoms return to the baseline will be recorded. Subjects should also record the date and time of recurrence, if any, of symptoms after they leave the clinic.

- A patient reported pruritus/hive score from 0 (none) to 3 (severe) for itch and hive using Uniform Assessment System (UAS) twice daily as below:

| Itch Severity Score | Amount of Itch | Itch Severity at Each Assessment |
|---------------------|----------------|--|
| 0 | None | None |
| 1 | Mild | Minimal awareness, easily tolerated |
| 2 | Moderate | Definite awareness, bothersome but tolerable |
| 3 | Intense | Difficult to tolerate |

| Hive Severity Score | Number of Hives at Each Assessment |
|---------------------|------------------------------------|
| 0 | None |
| 1 | 1-6 |
| 2 | 7-12 |
| 3 | >12 |

- Patient reported pain associated with the urticaria flare will be recorded based on a self-reported VAS score

- An investigator-rated extent of urticaria; % of body area with urticaria (Grade 1: urticarial lesions covering < 10% body surface area [BSA]; Grade 2: urticarial lesions covering 10-30% BSA; Grade 3: urticarial lesions covering > 30% BSA)
- An investigator-rated erythema score (0 = none, 1 = almost clear [slight redness], 2 = mild erythema [definite redness], 3 = moderate erythema [marked redness], 4 = severe erythema [fiery redness])

[REDACTED]

[REDACTED]

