10.1 Screening (Days -90 to -1)

The Investigator or his/her approved designee must explain the nature of the study protocol and associated risks to the potential study participant. The potential participant must be allowed to review the study information and to ask questions before being asked to sign the Informed Consent Form (ICF). Written informed consent must be provided by the potential study participant prior to initiation of any screening evaluations or other study-related procedures. The signature date and the name of the individual at the site who obtained the informed consent will be recorded in the subject's medical record.

After written informed consent is obtained, the subject will be assigned a screening number and will undergo the designated screening procedures listed in Appendix A. The Investigator, Sub-Investigator or delegate will assess the results of these screening evaluations to determine eligibility for entry into the study according to the inclusion/exclusion criteria listed in [Section 4.0](#).

Screening evaluations may be performed up to 90 days in advance of dosing but must be completed at least one (1) day prior to Day 0.

The following study evaluations and procedures are required to determine eligibility:

- Obtain and record a medical history, including demographics, prior medications, and concomitant medications.
- Complete PE
- Vital signs
- Height and weight measurements
- Blood and serum samples for the following laboratory evaluations:
 - Hematology
 - Serum chemistry
 - Coagulation
 - HIV antibody
 - Hepatitis screening
- Urinalysis, urine drug, alcohol and cotinine screen (Saliva test for alcohol may be utilized)
- Urine pregnancy test

- 12-lead ECG (performed in triplicate)

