10.2 Pre-dose Evaluations (Treatment Periods 1 - 3)

Subjects will return to the site when experiencing an acute flare of urticaria symptoms or chronic spontaneous urticaria before taking other acute medications. Urticaria symptoms and severity will be assessed based on both patient-reported and clinician-based assessments. Pre-dose assessments include the following:

- Admission to clinical site
- Confirm eligibility (Treatment period 1 only)
- Confirm medical history (Treatment period 1 only)
- Targeted PE
- Concomitant medications
- Vital signs
- Patient-reported pruritus/hive score and VAS for pain
- Investigator-rated extent of urticaria and erythema score

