10.3 Drug Administration

After baseline safety assessments, subjects will be randomized to receive the following treatments at each of the three Treatment Periods:

- 1 mg per 100 μ L dose of ARS-1,
- 2 mg per 100 μ L dose of ARS-1, or
- placebo (100 μ L)

ARS-1 or placebo will be dosed to the nostril by the medical professional in a clinical setting per IFU ([Appendix B](#)). [REDACTED]

[REDACTED] Subjects will be monitored for both safety and symptom relief. Safety assessments will be performed after dosing and will include AEs and vital signs. Concomitant medications will be recorded.

Subjects should remain in the clinic as below:

- Acute flare: at least 2 hours after dosing and can discharge when the discharge criteria is met (the time when symptoms of acute urticaria have been effectively treated based on the investigator's or his/her designee's opinion will be recorded, not necessarily when subjects discharged). If no relief of pruritus symptoms after 2 hours, other acute interventions may be administered as rescue.

- Chronic spontaneous urticaria: until the urticaria symptoms returns to the baseline. [REDACTED]

The calendar date and 24-hour clock time of all doses will be recorded on the eCRF.

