14.3 Efficacy Data Analyses

14.3.1 Primary Efficacy Analyses

The baseline for the primary endpoints will be the pre-dose at each visit.

Superiority comparison of ARS-1 1 mg vs. placebo and ARS-1 2 mg vs. placebo at each timepoint will be tested at the two-sided 0.05 significance level. If both ARS-1 1 and 2 mg are statistically superior to placebo, comparison between the ARS-1 doses will be conducted.

Time to effect is defined to be the time that it takes to lower one grade, two grades, and three grades.

Duration of effect is defined as the time from when the grade becomes above baseline until the grade returned to baseline.

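### The score ≥ 2 threshold describes the subject's usual week and is not, on the readable text, a condition for the flare that is dosed, so low-grade flares with little room to improve can use up a Treatment Period

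*Combined protocol and SAP*

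**What the plan says.** **Entry to the study.** Section 4.1, criterion 2 (repeated in the Synopsis) holds the only readable symptom-severity threshold: "have urticaria symptom (patient-rated pruritus and hive severity score ≥ 2) at least two (2) times a week", while on chronic treatment.

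**Entry to a Treatment Period.** Section 10.2 says: "Subjects will return to the site when experiencing an acute flare of urticaria symptoms or chronic spontaneous urticaria before taking other acute medications". Section 3.6 uses the same trigger. Neither gives a minimum score. The pre-dose list in 10.2 includes "Patient-reported pruritus/hive score and VAS for pain" in all three Periods, with no condition attached. The eligibility item in that list is limited to the first Period ("Confirm eligibility (Treatment period 1 only"), and Appendix A agrees.

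**Next step.** Section 10.3 goes straight on: "After baseline safety assessments, subjects will be randomized to receive the following treatments at each of the three Treatment Periods".

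**Measurement and analysis.** Section 3.3 defines "A patient reported pruritus/hive score from 0 (none) to 3 (severe) for itch and hive". Section 14.3.1 adds: "The baseline for the primary endpoints will be the pre-dose at each visit". It defines time to effect as the time to fall by one, two and three grades. The model in the Synopsis has treatment, period and subject terms and names no term for entry severity.

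**The concern.** Criterion 2 can be met by a subject whose flare on the day of dosing is mild. A flare may have eased by arrival, or a subject with chronic spontaneous urticaria may attend with mild itch and few hives. As written, that subject is dosed. Because each subject receives each treatment once, the mild flare is then that subject's only observation on that treatment.

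This matters because the itch and hive scales are short and bounded at zero. A low entry score caps the improvement that can be seen. Uneven entry severity across a subject's three Periods also adds noise to the within-subject comparison. A small difference from placebo could then reflect how little there was to treat.

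**Working it through.** The plan gives no figure to reproduce here. Section 14.1 bases the sample size on practical grounds, and no effect size, standard deviation or power is readable.

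**Step 1: floor of the scale (no assumption about the drug).** Inputs: item range 0-3 (3.3), baseline equal to the pre-dose score at each visit, and falls of one, two and three grades (14.3.1). A fall of k grades needs a pre-dose score of at least k.

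| Pre-dose item score | One-grade fall | Two-grade fall | Three-grade fall |
|---|---|---|---|
| 0 | no | no | no |
| 1 | yes | no | no |
| 2 | yes | yes | no |
| 3 | yes | yes | yes |

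The table applies to each item separately. Section 14.3.1 does not tie the word grade to a particular scale. If grades were counted on the itch + hive sum, itch 1 plus hives 1 could fall by two.

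**Step 2: what ≥ 2 admits.** Two items scored 0-3 give 4 × 4 = 16 combinations. Reading ≥ 2 as each item, 4 qualify. Reading it as the sum, 13 qualify, including itch 1 plus hives 1. The text of criterion 2 does not settle which is meant.

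**Step 3: shrinkage of the mean effect (assumed inputs).** Assume that the treatment removes a fixed fraction of the entry score, that qualifying flares average m, that a share f of flares enters at 1, and that this share is the same on each treatment. Then:

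relative mean effect = (1 − f) + f × (1/m), so loss = f × (1 − 1/m).

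| m | 1/m | Loss at f = 25% | Loss at f = 50% |
|---|---|---|---|
| 2 | 0.50 | 0.25 × 0.50 = 12.5% | 0.50 × 0.50 = 25% |
| 2.5 | 0.40 | 0.25 × 0.60 = 15% | 0.50 × 0.60 = 30% |
| 3 | 0.33 | 0.25 × 0.67 = 17% | 0.50 × 0.67 = 33% |

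A simulation with scores rounded and held within 0-3 gave a similar pattern. It assumed falls of 50% on active and 24% on placebo, noise SD 0.8, and 32 subjects. The mean difference was −0.60 grades with no flares at 1, −0.51 with 25% and −0.41 with 50%. That is 0.51/0.60 = 85% and 0.41/0.60 = 68% of the full difference.

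**Step 4: effect on power, for scale only.** With 32 pairs and a two-sided 0.05 paired t-test, 80% power needs a standardised within-subject difference of 0.51. Multiplying that by 0.85 and by 0.70 gives power of about 66% and 50%. The starting value of 0.51 is chosen to give 80% power; it is not the sponsor's assumption.

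**The case against.** **A flare already implies severity.** Criterion 2 attaches the threshold to urticaria symptoms, and 10.2 speaks of a flare of such symptoms, so ≥ 2 might be meant to carry over. This stands in part. A reader might infer that score-0 flares will fill Periods, but the documents do not support that for acute flares. The carry-over is nowhere stated, however, and it is weakest for chronic spontaneous urticaria, where having the condition is enough to attend.

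**Blacked-out text.** Section 12.4 (Administration of Study Drug) is in the contents but not readable, and parts of 10.3 and Appendix A are hidden. A hidden condition cannot be excluded. It is unlikely in 10.3, because the Synopsis shows the parallel text and the hidden places match its sentences on rescue medication and the follow-up call. The 10.2 list is readable and contains no such condition.

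**The history is assessed.** A reader might infer that criterion 2 is never checked. That goes too far: 10.1 introduces its list with "The following study evaluations and procedures are required to determine eligibility", and the list includes a medical history. What is absent from the readable screening items is an itch or hive score.

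**Other scales have room.** The endpoints under the primary objective include a 0-4 erythema score and a pain VAS. The cap in Step 1 applies to the itch or hive item concerned, not to every measure of that flare.

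**The study is exploratory.** The Synopsis says so, and baseline is reset at each visit. This lowers the stakes. Resetting the baseline does not create room to improve.

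**Conclusion.** The point holds on the readable text. The threshold is a study-entry criterion about the usual pattern, and nothing visible applies it to the flare being treated in any Period. The floor arithmetic follows from the documents alone: on a 0-3 item, entry at 1 rules out the two- and three-grade events.

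The size does not follow from the documents. The loss of about 15% to 30% rests on a proportional effect, a qualifying mean of 2.5, and 25% to 50% of flares entering at 1. None of these is given, so no particular loss of effect or power is shown for this trial.

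A reader might also take itch ≥ 2 together with hives ≥ 2 to be the protocol's own threshold. The wording does not establish that; it may mean the sum. The each-item reading would turn away a subject with itch 3 and 1-6 hives, who has ample room to improve on itch.

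**What to change.** Reconcile criterion 2 with Section 10.2 and Appendix A so that the sponsor's own ≥ 2 threshold becomes an entry condition for counting a flare as a Treatment Period, in each of Periods 1-3. It can be checked on the pre-dose scores already taken. State in criterion 2 whether ≥ 2 means each item or the itch + hive sum, noting that a sum of 2 admits itch 1 plus hives 1. The sponsor should set how a subject who does not qualify at a visit is handled.

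**Cost.** This is a wording amendment with no new assessment at dosing. Some visits will not lead to dosing, and some subjects may finish later or miss a Period. Two qualifying episodes a week over the 3-4-week study period in the Synopsis give 2 × 3 = 6 to 2 × 4 = 8 episodes for three doses. That leaves some slack, but it is an upper figure, because it supposes that every episode is attended and still qualifies on arrival. The mITT set needs efficacy data from at least two treatments, so a subject who misses one Period can stay in the efficacy analysis and one who misses two cannot.

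**What remains.** A three-grade fall stays possible only for items entering at 3, so that time-to-effect measure will still be unreachable for items entering at 2.

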4.2 Exclusion Criteria

Subjects must **NOT** meet any of the following Exclusion criteria to be eligible for enrollment:

- 1. Has a history of clinically significant gastrointestinal, renal, hepatic, neurologic, hematologic, endocrine, oncologic, pulmonary, immunologic, psychiatric, or cardiovascular disease or any other condition which, in the opinion of the Investigator, would jeopardize the safety of the subject or impact the validity of the study results.
- 2. Patients receiving beta blocker due to potential interaction with the study drug.
- 3. Has prior nasal fractures, severe nasal injuries or history of nasal disorders (e.g., polyps, polyposis, recurrent epistaxis [>1 nosebleed per month], clinically meaningful deviated septum, nasal piercing or any nasal passage abnormality based on the Investigator's judgement).
- 4. Has any clinically significant medical condition or physical exam (PE) finding as deemed inappropriate by the Investigator.
- 5. Has abnormal cardiovascular exam at screening including any prior history of myocardial infarction or clinically significant abnormal ECG (e.g., second- or third-degree heart block, uncontrolled arrhythmia, QTcF [Fridericia's correction] interval >450 msec for male subjects and >470 msec for female subjects).

6. Has mucosal inflammatory disorders (e.g., pemphigus or Sjogren's syndrome or fungal sinusitis).
7. Has had significant traumatic injury, major surgery or open biopsy within 30 days prior to study screening.
8. Has donated blood or had an acute loss of blood (>50 mL) during the 30 days before study drug administration or intends to donate blood or blood products within 30 days after the completion of the study.
9. Known hypersensitivity to any compound in the test product, or any other closely related compound (e.g., dihydropyridine-derived molecules).
10. Has participated in a clinical trial within 30 days prior to the first dose of study drug. Participation in an observational (non-interventional) study is not excluded as long as there are no scheduling conflicts with this study.
11. Has had treatment with any epinephrine or norepinephrine containing products within 7 days of Day -1.
12. At screening is positive for human immunodeficiency virus (HIV), Hepatitis B surface antigen (HbSAg), or Hepatitis C, or a positive urine screen for drugs of abuse or cotinine or a positive saliva test for alcohol.
13. Has an immediate family member of the Investigator, or an employee of the study center, with direct involvement in the proposed study, or other studies under the direction of the Investigator or study center or is in a dependent relationship with a study center employee who is involved in the conduct of this study (e.g., spouse, parent, child, sibling), or may consent under duress.

4.3 Stopping or Suspending the Study

If the trial is prematurely terminated or suspended for any reason, the Investigator/Institution should promptly inform the trial subjects, should assure appropriate therapy and follow-up for the subjects, and, where required by the applicable regulatory requirement(s), should inform the regulatory authority(ies).

In addition, if the Investigator or the Sponsor terminates or suspends a trial,

- the Investigator should inform the Institution where applicable, and the Investigator/Institution should promptly inform the Institutional Review Board/Ethics Committee (IRB/IEC) (and the Sponsor, if applicable) and should provide the Sponsor and/or the IRB/IEC a detailed written explanation of the termination or suspension.

- the Sponsor should promptly inform the Investigators/Institutions, and the regulatory authority(ies) of the termination or suspension and the reason(s) for the termination or suspension.

5.0 SCREENING ASSESSMENTS

5.1 Complete or Targeted Physical Examination

The Investigator will perform a complete PE at screening. A targeted PE will be performed at pre-dose in each Treatment Period. Results will be recorded on the appropriate page of the electronic case report form (eCRF).

5.2 Medical History

A medical history will be obtained at screening. Medical history will include demographic data (age, sex, race/ethnicity, etc.). The medical history will be confirmed at pre-dose in Treatment Period 1.

5.3 Vital Signs

Vital signs (BP, pulse rate [PR], respiratory rate, and temperature) are to be obtained at screening and pre-dose each Treatment Period.

5.4 Height and Weight

Height will be reported in centimeters at screening. Body weight will be reported in kilograms at screening.

5.5 ECG

Subjects will be in a sitting or slightly reclined position and kept comfortable for a standard (after resting for at least 5 minutes) 12-lead ECG that will be performed in triplicate by a trained technician at screening.

All ECGs are obtained in triplicate. ECG assessments will be conducted by taking a 10 second reading in triplicate, each 1 to 2 minutes apart for screening and baseline and within the window before and after dosing. Subjects will be in a sitting or slightly reclined position and kept comfortable.

ECGs will be assessed by the Investigator, Sub-Investigator or a cardiologist. The ECG report must be reviewed, signed, and dated by the Investigator or cardiologist. The original ECG results will be kept on file at the site as source documentation.

